**TRILUMINATE Pivotal CIP**  
(Version F)

## **6.4 Subject Enrollment**

A patient is considered enrolled in the clinical investigation from the moment the patient provides written informed consent and has been confirmed to meet all inclusion criteria and none of the exclusion criteria. .

Subjects will be assigned a subject ID upon informed consent and entry into the database. Such subjects are registered in the trial.

### **6.4.1 Enrollment of Medicare Beneficiaries**

This clinical trial will enroll appropriate Medicare beneficiaries that qualify based on the inclusion and exclusion criteria set forth in the trial. This IDE clinical trial adheres to all standards of Medicare coverage requirements set forth by the IDE and clinical trial coverage policies of the Center for Medicare and Medicaid Services (CMS). Section 16, Risks Analysis section, describes how all enrolled subjects, including Medicare beneficiaries, may be affected by the device under investigation.

Subjects enrolled in the clinical investigation are expected to be consistent with the Medicare population based on age range, demographic characteristics and cardiovascular risk factors representative of the Medicare patient population, so as such, the clinical investigation results are expected to be generalizable to the Medicare population.

### **6.4.2 Historically Under-Represented Demographic Subgroups**

The Sponsor intends to implement FDA's guidance on sex-specific data in medical device clinical investigations to ensure adequate representation of women and other traditionally under-represented demographic subgroups in this clinical investigation. To date, experience with transcatheter technologies for the tricuspid valve have shown the treatment population to be a majority female. As noted in the guidance, some barriers to participation of women and ethnic minorities in clinical investigations have traditionally been:

- Lack of understanding about main obstacles to participation of such subgroups in clinical research
- Inclusion/exclusion criteria potentially not needed to define the clinical investigation population may unintentionally exclude specific subgroups
- Under diagnosis of disease etiologies and pathophysiology leading to under referral of demographic subgroups
- Avoidance of specific subgroups by investigators and Sponsors due to the perception that it takes more time and resources to recruit them
- Fear of fetal consequences (for female participants)
- Family responsibilities limiting women's ability to commit time for follow-up requirements

The Sponsor will take the following steps to ensure adequate representation of women and racial or ethnic minorities in this clinical investigation:

- The Sponsor will provide training to investigational site personnel to ensure adequate representation of these demographic subgroups

**TRILUMINATE Pivotal CIP**  
(Version F)

- The Sponsor will regularly review enrollment data to investigate whether there is underrepresentation of these demographic subgroups
- The Sponsor will regularly review withdrawal rates for under-represented subgroups and compare these rates with that in the overall clinical investigation population
- As appropriate and necessary, the Sponsor will retrain sites on the importance of recruiting and retaining subjects in the clinical investigation
- The Sponsor will approach sites without bias or consideration for specific demographic subgroups
- The Sponsor will have informed consent materials in alternative languages and will work with sites and IRBs/ECs on recruitment materials

## **6.5 Subject Withdrawal**

Each enrolled subject shall remain in the clinical investigation until completion of the required follow-up period; however, a subject's participation in any clinical investigation is voluntary and the subject has the right to withdraw at any time without penalty or loss of benefit. Conceivable reasons for discontinuation may include, but not be limited to, the following:

- Subject death
- Subject voluntary withdrawal
- Subject lost-to follow-up as described below

The Sponsor must be notified of the reason(s) for subject discontinuation. The site will provide this information to the Sponsor. Investigators must also report this to their respective IRB/EC as defined by their institution's procedure(s).

No additional follow-up will be required or data recorded from subjects once withdrawn from the clinical investigation, except for the status (deceased/alive).

However, if a subject withdraws from the investigation due to problems related to the safety or performance of the device under investigation, the investigator shall ask for the subject's permission to follow his/her status/condition outside of the clinical investigation.

In case of subject withdrawal, the site should make attempts to schedule the subject for a final clinical investigation visit. At this final follow-up visit, the subject will undergo the following assessments:

- 12-lead ECG
- Blood draw (Same as required for follow-up visits)
- Physical exam including vital signs (weight, heart rate and blood pressure)
- Echocardiogram – TTE
- Modified Rankin Scale (Assessment of mRS should be done only after onset of stroke; not required after 12 months)
- 6-Minute Walk Test (6MWT) – See **APPENDIX XIII** for 6 Minute Walk Test Guidelines
- Concomitant cardiovascular medications assessment
- NYHA Functional Class assessment
- KCCQ QoL questionnaire to be completed by the subject – must be administered by “blinded” study personnel. Note: To minimize bias and undue influence, the QoL questionnaires will be completed by the subject, unless the subject is unable to

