### **4.2 Measures Taken to Avoid and Minimize Bias**

Due to the nature of the treatment in the two randomized groups, the subject, some site personnel and some Sponsor personnel will be aware of treatment assignment. The following steps will be taken to minimize bias in the conduct of the trial and analyses of clinical data.

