## **TRILUMINATE Pivotal CIP** (Version F)

- Sites should promptly reschedule any missed subject visits, and to reinforce the necessity of a follow-up visit to subjects.
- If a scheduled visit is missed due to subject illness, transportation issues, or travel, the site should:
  - Reinforce the necessity of follow-up visits;
  - Identify alternate transportation sources, and involve the Sponsor if necessary.
- Sites will be instructed to ask subjects who withdraw during the trial to provide the reason for withdrawal and ask them if the investigator may contact them to check their vital status at the end of the trial follow-up.
- Follow-up rates will be monitored closely so follow-up problems may be identified and addressed as soon as possible.
- For subjects lost-to-follow-up, sites may be requested to examine the Social Security Death Index to determine subject status (only the status will be sent to Sponsor, not any subject identifying information).

In addition to aforementioned steps, investigational sites will be educated on the importance of maintaining low rates of withdrawals in both Device and Control groups, and will be expected to make all efforts to maintain low withdrawals during trial conduct. If necessary, an independent service (e.g. Hawthorne Effect) may be utilized to provide in-home visits to aid in follow-up compliance. Withdrawals from the trial may need discussion between investigator and the Sponsor.

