## **5 ENDPOINTS**

### **5.1 Randomized Cohort**

#### **5.1.1 Primary Endpoint**

The primary endpoint is a hierarchical composite of all-cause mortality or tricuspid valve surgery, heart failure hospitalizations, and quality of life improvement assessed using the KCCQ at 12 months. The endpoint will be evaluated in a hierarchical order as follows:

- Time to all-cause death or tricuspid valve surgery
- Number of Heart Failure (HF) Hospitalizations
- An Improvement of  $\geq 15$  points in KCCQ from baseline

HF Hospitalization includes any of the following:

1) Hospitalization ( $\geq 24$  hours) with the primary reason for admission as acute decompensated HF and administration of intravenous or mechanical heart failure therapies, especially IV administration of diuretic therapy.

2) An unscheduled or unplanned admission to the emergency department, hospital outpatient observation unit, or hospital inpatient unit, and IV administration of diuretic therapy. Overnight stays for IV administration of diuretic therapy at nursing home facilities, physical rehab or extended care facilities, including hospice, will be included in the definition of hospitalization if related to heart failure.

3) Subject arrives in emergency department with clinical presentation meeting the criteria of HF, but dies in the emergency department before hospital admission.

Elective heart failure “tune-ups” that occur following the TriClip™ procedure and prolong hospitalization will not count as a heart failure hospitalization.

Based on the current experience, it is expected that the Device group may experience a mortality benefit, improved freedom from heart failure symptoms, as well as a quality of life improvement when their TR is treated.

Study Document No: ABT-CIP-10249

Study Name: TRILUMINATE Pivotal

**CONFIDENTIAL:** May not be reproduced outside of Abbott without written permission from Document Control. This is a quality record which will be retained per the local retention policy.

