### **7.11 TriClip™ Intervention in Control Group Subjects or Additional TriClip™ Intervention in Roll-in, Device Group or Single-arm Cohort Subjects**

Control group subjects will not be allowed to undergo the TriClip™ procedure until after completion of the 12-month visit. TriClip™ intervention in the Control group prior to the 12-month visit will be considered a major protocol deviation. Prior to TriClip™ procedure attempt in, a Control group subject upon completion of 12-month visit, the subject must be rescreened and evaluated by the ECL and EC to assess eligibility. A 30-Day Post-TriClip™ Follow-up visit must be completed 30 days (-3/+14 days) after the TriClip™ procedure. This visit should still be completed even if the subject is in hospital. The same assessments shall be performed as done for the 30-day follow-up. Following the 30-day post procedure visit the patient will continue with their predetermined visit schedule.

It may be necessary for a roll-in, Device group, single-arm, or cross-over subject to undergo additional TriClip™ procedures. A TTE must be performed within 90 days prior to a TriClip™ procedure in either group. A 30-day Post- TriClip™ Follow-up visit must be completed 30 days (-3/+14 days) after the additional TriClip™ procedure. This visit should still be completed even if

Study Document No: ABT-CIP-10249

Study Name: TRILUMINATE Pivotal

**CONFIDENTIAL:** May not be reproduced outside of Abbott without written permission from Document Control. This is a quality record which will be retained per the local retention policy.

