2.2.3 Survival Analyses

Survival analysis will be conducted to analyze time-to-event variables. Subjects without events will be censored at their last known event-free time point when they stay in the study. Survival curves will be

Statistical Analysis Plan

constructed using Kaplan-Meier estimates.

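### After withdrawal only alive-or-dead status is recorded, so tricuspid valve surgery, tricuspid valve intervention and heart failure hospitalizations in withdrawn subjects are never counted

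*Protocol*

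**What the plan says.** On withdrawal, Protocol 6.5 states: "No additional follow-up will be required or data recorded from subjects once withdrawn from the clinical investigation, except for the status (deceased/alive". A final visit is to be attempted, but it can cover only the period up to leaving. There is one exception. When the reason is a safety or performance problem with the device, "the investigator shall ask for the subject's permission to follow his/her status/condition outside of the clinical investigation". That follow-up lies outside the trial.

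Protocol 4.2.7 has sites ask withdrawing subjects for their reason and "ask them if the investigator may contact them to check their vital status at the end of the trial follow-up". For subjects lost to follow-up it adds a death-index check, which is again vital status only.

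The first two tiers of the primary endpoint (Protocol 5.1.1) are "Time to all-cause death or tricuspid valve surgery" and "Number of Heart Failure (HF) Hospitalizations". The two 24-month secondary endpoints (Protocol 5.1.2) are recurrent heart failure hospitalizations, and freedom from death, tricuspid valve surgery and tricuspid valve intervention. The primary analysis is ITT (SAP 2.3.1.1).

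On assignment, Protocol 4.2 says "the subject, some site personnel and some Sponsor personnel will be aware of treatment assignment". Protocol 7.11 says "Control group subjects will not be allowed to undergo the TriClip™ procedure until after completion of the 12-month visit".

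**The concern.** An ITT comparison depends on outcomes being known whether or not a subject keeps attending. Here one tier of the primary endpoint has two ascertainment rules: a withdrawn subject's death can still count, and a withdrawn subject's valve surgery cannot. The gap is in collection, so no analysis rule, readable or redacted, can recover the date of an operation that was never recorded.

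This would matter little if withdrawal were rare and unrelated to arm or prognosis. In an open-label trial that holds one arm back from the device for a year, that cannot be taken for granted. SAP 2.2.3 says of time-to-event variables: "Subjects without events will be censored at their last known event-free time point when they stay in the study". If leaving is related to prognosis or to plans for valve treatment, that censoring is informative.

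**Working it through.** **1. What remains observable after withdrawal** (Protocol 6.5 and 4.2.7 set against 5.1.1 and 5.1.2)

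| Event | Where it counts | Obtainable after withdrawal? |
|---|---|---|
| Death | Tier 1; 24-month composite | Yes |
| Tricuspid valve surgery | Tier 1; 24-month composite | No |
| Heart failure hospitalization | Tier 2; 24-month recurrent-event endpoint | No |
| Tricuspid valve intervention | 24-month composite | No |

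The 12-month KCCQ (tier 3) is not collected after withdrawal either. No readable section overrides this.

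**2. Is there an arm-specific reason to leave?** Subjects know their arm (Protocol 4.2). Controls may not have TriClip before the 12-month visit (7.11). The device is market released in the EU (3.2.1, Appendix XV). Together these make differential withdrawal plausible, but the documents do not state it. Three limits apply.
- The bar covers TriClip only. Section 7.12 allows tricuspid surgery in either arm, if the heart failure specialist and surgeon deem it required, with follow-up continuing.
- The device is investigational in the USA and Canada, and at least 50% of each cohort is US (Section 4). The commercial route is therefore open to at most half of subjects.
- After the 12-month visit Controls may cross over inside the trial, so the motive belongs mainly to the first year.

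**3. Exposure.** 350 subjects randomized 1:1 give 175 per arm and 175 × 175 = 30,625 Device-Control pairs. Each withdrawn Control enters 175 of them. The withdrawal rate is an assumption:
- 2% (3 subjects): 3 × 175 = 525 pairs, 1.7%
- 5% (9 subjects): 9 × 175 = 1,575 pairs, 5.1%
- 8% (14 subjects): 14 × 175 = 2,450 pairs, 8.0%

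This counts pairs touched. Pairs already decided by a death or by an event before withdrawal do not change, so it is a ceiling on exposure and not a bias.

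**4. Size on the primary endpoint.** The plan's approximately 83% power at 350 subjects (SAP 2.4.1.1) cannot be reproduced, because its component and attrition assumptions are redacted. As a substitute, a Finkelstein-Schoenfeld simulation was run with 175 per arm, 1,500 runs per scenario, and the variance formula in SAP 2.3.1.1. All inputs are assumptions (Device/Control):
- 12-month death 10%/13%
- tricuspid surgery 2%/5%
- heart failure hospitalizations 0.35/0.55 per year
- KCCQ responders 45%/27%
- withdrawal 3% in Device, and 5%, 10% or 15% in Control
- surgery hazard after withdrawal unchanged or five times higher

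Uncollected surgery was scored as no event and missing KCCQ as no improvement.

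| Control withdrawal | Surgery hazard after leaving | Control surgeries unseen / total | Device surgeries unseen | Power, full data | Power, vital status only |
|---|---|---|---|---|---|
| 5% | unchanged | 0.22 / 8.26 | 0.05 | 0.924 | 0.917 |
| 5% | ×5 | 0.93 / 8.95 | 0.25 | 0.937 | 0.917 |
| 10% | unchanged | 0.39 / 8.25 | 0.06 | 0.934 | 0.921 |
| 10% | ×5 | 1.90 / 9.79 | 0.25 | 0.932 | 0.923 |
| 15% | unchanged | 0.58 / 8.26 | 0.05 | 0.926 | 0.913 |
| 15% | ×5 | 2.80 / 10.37 | 0.24 | 0.949 | 0.927 |

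The loss is asymmetric but small, and power falls by 0.7 to 2.2 points. The Monte Carlo standard error of one power value is √(0.93 × 0.07 / 1,500) = 0.0066. For a difference it is 0.0066 × √2 = 0.0093, about 0.9 points. All six differences have the same sign, but singly they are not much above noise. The full-data runs also restore KCCQ, which the fix below would not.

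**5. Direction.** Under the scoring used here, unseen Control events shift the comparison against the device. The plan's own handling of missing data (Protocol 9.7, SAP 2.9) and its ITT definition are redacted, so the actual direction cannot be settled. No calculation was made for the 24-month endpoints. They have twice the follow-up window, depend on the uncollected events, and by name include the procedure a Control might leave to obtain.

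**The case against.** The strongest reply is that the mechanism is weak for the primary endpoint. A reader might infer that first-tier surgery is lost precisely when it is the reason for leaving. The documents do not support that: Protocol 7.12 lets either arm have surgery and stay in follow-up. What Controls are denied is TriClip, and TriClip is not a primary-endpoint event. Surgery is one of two listed first-tier components, but Protocol 2.1.1 calls isolated tricuspid surgery rare, so it need not be a large share of events. This part of the reply stands.

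A reader might also infer that contamination of the Control arm could not be measured or reported. That is too strong. Withdrawal reasons go to the sponsor (Protocol 6.5) and early-termination reasons are tabulated by treatment group (SAP 3.3). Early TriClip in a Control is a major protocol deviation (Protocol 7.11), and nothing says it ends participation. Section 4.2.7 also lists real retention measures, including in-home visits and education on low withdrawal in both arms. What stays unseen is whether and when a procedure or heart failure hospitalization followed withdrawal.

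Finally, stopping collection respects voluntary participation, and the analysis rules for withdrawn subjects are redacted. Both are true. The first is met by asking permission. The second limits what can be said about direction, but does not alter what is collected.

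**Conclusion.** The point holds as a collection gap with a cheap remedy. Protocol 6.5 and 4.2.7 leave death observable after withdrawal while tricuspid valve surgery, tricuspid valve intervention and heart failure hospitalizations are not. The effect on the 12-month primary is probably small: on assumed rates, up to about 3 Control surgeries and about 2 points of power in the most extreme scenario (15% Control withdrawal and a fivefold surgery hazard). The pair percentages measure exposure and should not be read as bias. The case is stronger for the two 24-month secondary endpoints, though it was not quantified. Differential withdrawal by arm is an inference about TriClip in the first 12 months, mainly outside the USA and Canada. The direction of any effect cannot be determined from the readable text.

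**What to change.** In Protocol 6.5 and 4.2.7, ask every withdrawing subject, in either arm and whatever the reason, for permission to go on collecting the following from medical records or by phone through 24 months: vital status, tricuspid valve surgery, any transcatheter tricuspid intervention (including commercial TriClip) and heart failure hospitalizations. If the subject refuses, keep vital status only, as now. State in the SAP that these events, CEC-adjudicated where applicable, enter the ITT analyses of the primary and 24-month endpoints. Alongside the early-termination table in SAP 3.3, tabulate valve treatment after withdrawal by arm.

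The cost is protocol and consent wording, one item on the withdrawal form and occasional record requests. A Tricuspid Valve Surgery Form (Protocol 7.13), withdrawal data capture (Table 1) and CEC adjudication of heart failure hospitalizations (Protocol Section 4) already exist. Some subjects will refuse, so the gap narrows but does not close.

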## TRILUMINATE Pivotal CIP (Version F)

complete the questionnaire on their own (a note to file must be completed to document the inability of subject to complete the questionnaire)

- Assess and record adverse events
- Assess and record protocol deviations

### Lost-to-Follow-up

If the subject misses two consecutive scheduled follow-up time points and the attempts at contacting the subject detailed below are unsuccessful, then the subject is considered lost-to-follow-up. Site personnel shall make all reasonable efforts to locate and communicate with the subject (and document these efforts in the source documents), including the following, at each contact time point:

- A minimum of three telephone calls over a period of 10 days to contact the subject or his/her relative/caregiver (where allowed per local regulations) should be recorded in the source documentation, including date, time and initials of site personnel trying to make contact.
- If these attempts are unsuccessful, a letter (certified if applicable) should be sent to the subject. The registered letter will request the subject to contact the site.
- If the above attempts are unsuccessful, the patient's general practitioner shall be contacted to investigate about the subject's whereabouts and his/her health status (where allowed per local regulations).

If a subject misses one or more non-consecutive follow-up contact time points, it will be considered a missed visit. The subject may then return for subsequent visits. If the subject misses two consecutive time points and the above-mentioned attempts at communicating with the subject are unsuccessful, the subject will be considered lost-to-follow-up.

Note: Telephone contact with General Practitioner, non-clinical investigation cardiologist or relative without the presence of the subject or indirect documentation obtained via discharge letters will not be considered as subject contact.

### **6.6 Total Expected Duration of the Clinical Investigation**

The clinical investigation duration is expected to be approximately 11 years, including 6 years for enrollment and 5 years of follow-up.

### **6.7 Expected Duration of Each Subject's Participation**

Each subject will be expected to participate for a duration of five years from Treatment visit.

### **6.8 Number of Subjects**

Approximately 450 subjects will be enrolled in the clinical investigation and randomized 1:1 to either the Device Group or to the Control Group. Enrollment into the Randomized cohort will continue until (1) the sample size re-estimation results are received and (2) enrollment meets the re-estimated sample size. The Single-arm cohort will enroll up to 200 eligible subjects, with enrollment continuing until the Randomized cohort has completed enrollment. Up to 3 roll-in subjects will be permitted per implanter without prior experience with the TriClip™ device.

Study Document No: ABT-CIP-10249

Study Name: TRILUMINATE Pivotal

**CONFIDENTIAL:** May not be reproduced outside of Abbott without written permission from Document Control. This is a quality record which will be retained per the local retention policy.

No site may enroll more than 25% of the total subjects.

